Subjects who discontinue study treatment for any reason (e.g., toxicity) other than disease progression should be followed until documented disease progression or start of a new anti-cancer therapy. All subjects will be followed for survival until death, loss to follow-up, or study completion.

Study completion is 3 years after the last subject starts study drug regimen.

Study Drug Regimen

In the Safety Validation Cohort, the cycle length is 21 days. Patients will receive pembrolizumab and oxaliplatin on day 1 of each cycle. Capecitabine will be taken twice per day on days 1-14 of each cycle. Patients will continue to receive study treatment until they experience unacceptable drug-related toxicity or disease progression.

In the Dose Expansion Cohort (ie. phase II), the first cycle of treatment, referred to as 'biomarker cycle,' will be modified to allow assessment of biomarkers related to pembrolizumab; the length will be 28 days. Patients will receive pembrolizumab monotherapy on Cycle 1 Day 1. Treatment with oxaliplatin and capecitabine will begin on Cycle 1 Day 8; capecitabine will be dosed for 14 days (ie. Days 8-21), followed by one week off drug (ie. Days 22-28). Cycle 2 will start on Day 29 of study (ie. 28 days after pembrolizumab monotherapy and 20 days after start of capecitabine and oxaliplatin). For cycles 2 and beyond, the cycle length is 21 days, with a treatment window of +/-3 days allowed for day 1. Patients will receive pembrolizumab and oxaliplatin on day 1 of each cycle. Capecitabine will be taken twice per day on days 1-14 of each cycle. Patients will continue to receive study treatment until they experience unacceptable drug-related toxicity or disease progression.

For both cohorts, patients will continue to receive study treatment until they experience unacceptable drug-related toxicity or disease progression. The maximum duration of treatment for pembrolizumab will be up to two years (35 cycles). The duration of treatment for capecitabine and oxaliplatin will be until unacceptable drug-related toxicity or disease progression. Patients who complete 35 cycles of therapy and have complete response or prolonged stable disease may also elect to end therapy with capecitabine, after a discussion with their treating physician.

Study Assessments

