2.0 OBJECTIVES

2.1 Primary Objective

The primary objective of this trial is:

1. To describe the progression free survival (PFS) associated with the combination of pembrolizumab, oxaliplatin and capecitabine (pembro+XELOX) in all patients with previously untreated metastatic esophagogastric adenocarcinoma.

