3.0 STUDY DESIGN

3.1 Study Description

This is a single arm, phase II study to assess the safety, tolerability, and efficacy of the recommended phase II dose (RPTD) of the combination of pembrolizumab, oxaliplatin and capecitabine in patients with previously untreated metastatic esophagogastric adenocarcinoma. The study will be conducted in two stages: 1) safety validation and 2) dose expansion. Approximately 50 subjects may be accrued to ensure the trial obtains 5 evaluable subjects in the safety validation cohort and 30 evaluable subjects in the dose expansion cohort. Patients will be enrolled at the Duke Cancer Institute and select external collaborating institutions (dose expansion cohort only).

- Enrolled subjects are defined as subjects who give informed consent.
- Screen failures are defined as subjects who give informed consent and do not meet eligibility criteria.
- Accrued subjects are defined as subjects who give informed consent and meet eligibility criteria.
 - Withdrawal: Subject accrued but later withdrawn from the study, either before or after receiving a study drug.
 - Evaluable: In the Safety Validation Cohort, subjects who are accrued, received study treatment, and completed the first cycle of safety assessments or have dose limiting toxicity (DLT) which is study treatment related that precludes completing the full cycle of assessments will be considered evaluable for DLT. All subjects (in Safety Validation and Dose Expansion) who are accrued and receive any study treatment will be considered evaluable for toxicity. All subjects in Safety Validation and Dose Expansion who are accrued and receive any study treatment will be considered evaluable for efficacy.
 - Non-evaluable: In the Safety Validation Cohort, subjects who accrued but did not complete the first cycle of safety assessments due to reasons other than study treatment-related toxicity (e.g. disease progression or inter-current illness) are considered non-evaluable for DLT.

Table 3.1 Cohorts

Cohort	No. Evaluable Subjects	Oxaliplatin mg/m ² IV, Day 1 every 21 days*	Capecitabine mg/m ² PO, BID Days 1-14 every 21 days*	Pembrolizumab mg IV, Day 1 every 21 days*
Safety Validation	5	130	850 or 1000**	200
Dose Expansion	30	130	850 or 1000**	200

*For dose expansion cohort, Cycle 1, biomarker cycle, is 28 days in length. Cycles 2 and beyond are 21 days.

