3.3 Dose Expansion Cohort

Once 5 evaluable subjects have been treated in the safety validation cohort with no more than one occurrence of DLT as defined in Section 3.2.1, the second portion of the study (ie. phase II) will accrue

30 evaluable patients to assess the safety, tolerability, and efficacy of the RPTD of the combination of pembrolizumab, oxaliplatin and capecitabine in patients with previously untreated metastatic esophagogastric adenocarcinoma. Subjects on this portion of the study will be enrolled at the Duke Cancer Institute and select external collaborating institutions.

In the dose expansion cohort, the first cycle will be modified to allow one week of pembrolizumab monotherapy before starting XELOX chemotherapy, which will allow analysis of biomarkers related to pembrolizumab; thus Cycle 1 for the dose expansion cohort will be 4 weeks.

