5.3 Follow-up Period

Subjects should return 30 (\pm 7) days after their last dose of study drug for an off-treatment visit to complete the following study procedures:

- Physical examination
- Vital signs and weight
- Concomitant medications
- ECOG performance status
- Adverse event assessment
- CBC with differential
- Chemistries including LFTs
- Thyroid function tests
- Serum pregnancy test (only for women of childbearing potential)
- Plasma
- Archived tissue collected at end of study (if available)

Additional follow-up may occur for subjects with adverse events (AEs) related to study drug that are ongoing at the time of this off-treatment visit unless AE is deemed unresolvable or subject has started a new anti-cancer treatment regimen.

For subjects that are discontinued from study treatment for reasons other than disease progression, subjects will have disease status (blood tumor marker(s) and restaging scans per standard of care schedule) followed until disease progression or start of new anti-cancer treatment regimen. Disease status may be collected by personal interviews or review of medical records. Disease progression follow up will continue for as long as patient is in survival follow up, provided they have not progressed or started a new anti-cancer treatment. For subjects that completed therapy and remain in complete response, PBMCs and plasma will be collected approximately every three months with standard of care visits, provided subjects consent to this additional follow-up.

Subjects will be followed for survival up to 3 years after the last subject starts the study drug regimen or until the study is closed (whichever comes first). Survival status may be collected by phone call or review of medical or public records approximately every 12 weeks.

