9.1.1 Primary Endpoint

The primary endpoint will be progression-free survival (PFS) measured from study entry until documented progression or death from any cause. Patients who have not experienced progression will be censored at the date of the last radiographic assessment. Based on the results of the AVAGAST and ToGA trials a median PFS of approximately 5.5 months is expected for patients treated with oxaliplatin and capecitabine alone. Also, observed PFS hazard ratios of 0.80 and 0.71 were reported for AVAGAST and ToGA, respectively. With 35 patients enrolled, the difference between a historical median PFS of 5.5 months and experimental median of 7.3 months, a hazard ratio of 0.75, can be detected with 80% power (1-sided test of single exponential mean, $\alpha=0.2$).

PFS and median PFS will be estimated using the Kaplan-Meier method. The 95% confidence interval estimate for median PFS will be computed using the variance estimate proposed by Brookmeyer and Crowley. Under the alternative hypothesis, 32 PFS events are expected at the end of the follow-up period.

The primary analysis of PFS will be intention-to-treat in that all patients who have undergone at least one scheduled restaging on-treatment, or who have had unequivocal progression prior to the first scheduled restaging will be followed for progression. These patients will be followed for PFS, even if they are removed from treatment due to unacceptable toxicity or because they withdrew consent. As a secondary analysis, these patients will be censored at the time they were removed from treatment.

The magnitude of reduction in tumor burden will be summarized descriptively (such as a waterfall plot) based on change in the sum of the longest diameters of target lesions relative to baseline.

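### The primary PFS analysis is called intention-to-treat, but its definition leaves out a treated patient who dies before the first restaging without documented progression

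*Combined protocol and SAP*

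**What the plan says.** Section 9.1.1 defines PFS as "measured from study entry until documented progression or death from any cause". It then calls the primary analysis intention-to-treat and explains the term by naming who is followed for progression: "all patients who have undergone at least one scheduled restaging on-treatment, or who have had unequivocal progression prior to the first scheduled restaging". The next two sentences refer back to the same group. These patients are followed for PFS even after removal from treatment, and a secondary analysis censors them at removal. The censoring rule is "Patients who have not experienced progression will be censored at the date of the last radiographic assessment".

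Other sections describe the population differently. Section 3.1 states: "All subjects in Safety Validation and Dose Expansion who are accrued and receive any study treatment will be considered evaluable for efficacy". Section 2.1 sets out to describe PFS "in all patients with previously untreated metastatic esophagogastric adenocarcinoma". Section 9.1 plans for 35 evaluable patients, enrolled and treated.

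On follow-up, the Synopsis states: "All subjects will be followed for survival until death, loss to follow-up, or study completion". For patients who stop treatment without progression, Section 5.3 adds: "Disease progression follow up will continue for as long as patient is in survival follow up", as long as they have not progressed or started new anti-cancer treatment.

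**The concern.** Membership of the primary set depends on something that happens after treatment starts: reaching a restaging, or progressing before it. Death is a PFS event but does not qualify a patient for the set. A patient who dies in the first two months without documented progression therefore has the worst possible outcome and is not counted.

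There is no control arm in which the same omission would occur. The estimate is set beside a fixed historical median, so an upward shift reads directly as benefit. Sections 3.1 and 9.1.1 also give two different primary sets, and nothing prevents the choice being made after the data are seen.

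Patients who stop early without progression are a different case. Section 5.3 already follows them, and leaving them out has no certain direction. It has no effect on the Kaplan-Meier curve if they would be censored at baseline anyway.

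**Working it through.** **1. One patient under each rule.** Take a treated patient who dies in week 6, with no scan after baseline and no documented progression.

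| Text | Treatment of this patient |
|---|---|
| 9.1.1, PFS definition | Event at death |
| 9.1.1, intention-to-treat sentence | Outside the named group |
| 9.1.1, censoring sentence, read literally | No progression, so censored at the last scan, which is baseline |
| 3.1, evaluability | Included for efficacy |

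Censoring at baseline and excluding the patient give the same Kaplan-Meier median (checked numerically). Correcting the set without the censoring sentence could therefore leave the problem in place.

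**2. The plan's own figure.** Inputs from 9.1.1: medians 5.5 and 7.3 months, 35 patients, one-sided alpha 0.2. The test of a single exponential mean rejects when 2·λ₀·(total time) > χ²(0.80; 2d), with λ₀ = ln 2/5.5 and d events. Power is P(χ² with 2d df > HR × critical value). With d = 35, power is 0.803 at HR 0.75 and 0.796 at HR 5.5/7.3 = 0.753. The stated 80% reproduces, and it counts all 35 patients.

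**3. The window.** The first restaging follows three cycles: 63 days for the 5 safety patients. Section 3.3 says "thus Cycle 1 for the dose expansion cohort will be 4 weeks", so for the 30 expansion patients it is 28 + 21 + 21 = 70 days. At 30.4375 days per month these are 2.07 and 2.30 months. With exponential PFS and a true median of 5.5 months (no drug effect):

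- P(event before restaging) = 1 − 2^(−t/5.5) = 0.230 and 0.252.
- Expected early events = 5 × 0.230 + 30 × 0.252 = 8.7 of 35.

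Only those early events that are deaths without documented progression are lost. The documents do not give that share, so the number lost, k, is varied from 1 to 4. That is about 11%, 23%, 34% and 46% of the 8.7.

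**4. Apparent median.** Removing k early events from 35 multiplies survival after the window by 35/(35 − k). The apparent median solves S(t) = 0.5·(35 − k)/35, so t = −5.5·log₂[0.5·(1 − k/35)]. For k = 2: 0.5 × 33/35 = 0.4714, and −5.5 × log₂(0.4714) = 5.97.

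**5. Error rate.** The test in step 2 was simulated 60,000 times with uniform 12-month accrual, 36 to 48 months of follow-up and no replacement.

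| k excluded | Apparent median (months) | One-sided error (nominal 0.20) |
|---|---|---|
| 0 | 5.50 | 0.202 |
| 1 | 5.73 | 0.245 |
| 2 | 5.97 | 0.293 |
| 3 | 6.21 | 0.346 |
| 4 | 6.46 | 0.405 |

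A separate simulation dropped a random share of the events before week 9. Shares of 10%, 25% and 50% (0.8, 2.0 and 4.0 patients on average) gave error rates of 0.23, 0.295 and 0.41, which agrees.

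**6. Scale.** The planned gain is 7.3 − 5.5 = 1.8 months. The simulated Kaplan-Meier median of 35 patients has a 95% range of about 3.3 to 8.5 months with none excluded. The mean shift is +0.47 month for k = 2 and +0.95 for k = 4.

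**The case against.** The strongest reply is that the exclusion is inferred. The sentence says the named patients will be followed for progression, and the text after it suggests that intention-to-treat here means following patients regardless of stopping treatment. A patient who has died needs no such follow-up. The event definition, Section 3.1 and the use of 35 in the power statement all point towards counting early deaths. It is true that the exclusion is not stated outright. But the sentence opens as a description of the primary analysis, and nothing else in Section 9 restores these patients. If Section 3.1 is meant to govern, the plan still holds two definitions that must be reconciled.

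Several narrower points stand in part:

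- The wording of the objective describes a disease population and does not define an analysis set. It is the weakest of the conflicting texts.
- Entry requires ECOG 0 or 1 and adequate organ function, so k = 3 or 4 has no support in the documents. These values only show the range.
- The exponential test appears only in the sample-size statement. The planned analysis is a Kaplan-Meier median with a 95% interval, so the shift in the median matters more than the error rate.
- Section 5.2 allows restaging every 3 ± 1 cycles, while Appendix D gives ± 1 week. With a one-cycle tolerance the 8.7 early events become 6.3 to 10.9.
- Section 5.3 ends progression follow-up at new therapy, so progression is not tracked in everyone. This does not affect the counting of early deaths, because survival is followed for all subjects.

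**Conclusion.** The concern holds. Read plainly, Section 9.1.1 leaves out treated patients who die before the first restaging without documented progression, against its own event definition and against Section 3.1. The error can only favour the regimen. One or two exclusions would add about 0.2 to 0.5 month to an apparent 5.5-month median, which is modest beside chance variation. Four would add about 1 month, more than half of the 1.8-month target. These sizes rest on exponential PFS, no replacement and an assumed number of early deaths. If no such death occurs there is no numerical effect, but the contradiction remains. The stated sample size and power are not in error. Because this decides who is counted in the only primary endpoint, it should be settled before the data are analysed.

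**What to change.** Amend Section 9.1.1 as follows:

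- Define the primary PFS set as all accrued patients who receive any study treatment, matching Section 3.1.
- Count a death before the first restaging as an event on the date of death.
- Apply censoring only to patients who are alive and without documented progression, and state the censoring date for those with no scan after baseline.
- State how patients who start new anti-cancer therapy before progression are handled, since Section 5.3 stops progression follow-up there.
- Keep the restaging-based set as a sensitivity analysis.

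This is a wording change. Survival follow-up already captures the deaths, so no extra data are needed. With 35 patients analysed and every death counted, the simulated error rate is 0.20 and power 0.795, as designed. The cost is that the estimated median PFS may be slightly shorter.

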9.1.2 Secondary Endpoints

Secondary endpoints include the safety and tolerability of the XELOX/pembrolizumab regimen and response rate (RR). Adverse events will be described and presented by Type and Grade according to NCI-CTCAE version 4.03 criteria and descriptively compared with historical controls.

Radiographic imaging will be repeated every three cycles (approximately every 9 weeks) as described in Section 5.0. Tumor response defined as complete response (CR) or partial response (PR) will be assessed using RECIST 1.1 (see Section 5.6).

RR will be estimated by the 90% confidence interval for the binomial proportion. With 35 patients studied (5 in the safety validation and 30 in the expanded cohort), RR can be estimated to within at most +/- 0.14 with 90% confidence.

The magnitude of reduction in tumor burden will be summarized descriptively (such as with a waterfall plot) based on change in the sum of the longest diameters of target lesions relative to baseline.

Overall survival (OS) will be described.

9.1.3 Exploratory Endpoints

CD8 and PDL1 staining measured by IHC are the primary biomarker endpoints for this study. Descriptive statistics will be provided for each of these endpoints at each time point (pre-, P, and on-treatment, OT) and for the change P vs OT.

For continuous CD8 and PDL1 expression measures (e.g., percentages), the paired t-test will be used to compare change in P vs OT. We expect approximately 25 patients to have paired measurements. With 25 patients studied a difference of 0.53 standard deviation (SD) can be detected with 90% power (1-sided $\alpha=0.1$). With this sample size differences of 13%, 27%, and 40% can be detected with 80% power assuming SDs of 0.25, 0.5, and 0.75, respectively.

For dichotomous paired proportions (e.g., <2+ versus >2+ by IHC) McNemar's test will be used to test the null hypothesis that the difference in P and OT proportions is 0 versus the alternative that it is > 0 or < 0. With 25 paired patient samples studied 79% power is achieved to detect the difference illustrated in Table 1a below and 86% power is achieved to detect the difference illustrated in Table 1b (2-sided $\alpha=0.1$).

Table 1a: Alternative hypothesis resulting in 79% power using McNemar's test (2-sided $\alpha=0.1$).

	Post Treatment		Total
Pre Treatment	<2+	>2+	
<2+	0.15	0.45	0.60
>2+	0.10	0.30	0.40
Total	0.25	0.75	1.00

Table 1b. Alternative hypothesis resulting in 86% power using McNemar's test (2-sided $\alpha=0.1$).

	Post Treatment		Total
Pre Treatment	<2+	>2+	
<2+	0.10	0.50	0.60
>2+	0.10	0.30	0.40
Total	0.20	0.80	1.00

Similar analyses will be conducted for other biomarkers as described in Section 8.0. No adjustments will be made for multiple comparisons. Data transformations or non-parametric methods will be used as appropriate.

Associations between changes in immune infiltrates and outcomes (PFS, RR, OS) will be explored using Cox regression (PFS), 2-sample t-tests or non-parametric Wilcoxon rank-sum tests, or the Chi-square test (6-month PFS, RR) based on the distribution and structure of the data (i.e., either parametric or non-parametric methods will be used as appropriate).

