2.3 Exploratory Objectives

The exploratory objectives of this trial are:

1. To explore changes in CD8 and PDL1 expression in tumor tissue related to pembrolizumab treatment.
2. To explore other changes in tissue and blood based biomarkers and their correlation with clinical outcomes.
3. To explore changes in immune cells and biomarkers in those who completed treatment and remain in complete response.

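### The paired t-test for CD8 and PDL1 is powered one-sided with no direction named, and the next sentence gives the same effect 80% power instead of 90%

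*Combined protocol and SAP*

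**What the plan says.** The objective in Section 2.3 is "To explore changes in CD8 and PDL1 expression in tumor tissue related to pembrolizumab treatment"; it gives no direction. Section 9.1.3 gives these markers some standing: "CD8 and PDL1 staining measured by IHC are the primary biomarker endpoints for this study". For continuous measures, "the paired t-test will be used to compare change in P vs OT". On numbers, "We expect approximately 25 patients to have paired measurements", and with that many "a difference of 0.53 standard deviation (SD) can be detected with 90% power (1-sided" alpha 0.1).

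The following sentence keeps the same sample size and lists differences of 13%, 27% and 40% as detectable with 80% power when the SD is 0.25, 0.5 and 0.75. It does not repeat an alpha or a sidedness.

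For staining scored as two categories, McNemar's test has a null of no difference "versus the alternative that it is > 0 or < 0", at two-sided alpha 0.1. Its power is given as 79% (Table 1a) and 86% (Table 1b). The section then adds: "Similar analyses will be conducted for other biomarkers as described in Section 8.0".

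**The concern.** A one-sided test is defined only once its direction is fixed, and no section says whether the t-test looks for a rise or a fall in CD8 or in PDL1. The objective is non-directional, and the companion test on the same stains allows change either way. The continuous and categorical analyses of one marker are therefore planned on different footings, with no reason given.

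The two adjacent power statements for the t-test also do not fit together. They describe nearly the same standardised effect and the same number of pairs, yet one gives 90% and the other 80%. A reader cannot tell which test will be run, or which power to believe.

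**Working it through.** **Inputs, all from Section 9.1.3.** Pairs n = 25; effect 0.53 SD; alpha 0.1 one-sided for the t-test; alpha 0.1 two-sided for McNemar's test; differences and SDs of 13%/0.25, 27%/0.5 and 40%/0.75 in the 80% sentence; discordant proportions 0.45 and 0.10 (Table 1a), 0.50 and 0.10 (Table 1b).

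**Method for the t-test.** Under an effect of d SDs, the paired t statistic has a noncentral t distribution with n − 1 = 24 degrees of freedom and noncentrality d√n. Power is the probability of passing the critical value: 1.318 for one-sided 0.1, and 1.711 for two-sided 0.1 or one-sided 0.05.

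**Step 1: the plan's 90%.** Noncentrality = 0.53 × √25 = 2.65. Power at one-sided 0.1 is 90.7%. The stated figure reproduces.

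**Step 2: the same effect at McNemar's level.** At two-sided 0.1 the power for 0.53 SD is 82.4%. Solving for 90% power with 25 pairs gives 0.52 SD one-sided and 0.60 SD two-sided. Keeping 0.53 SD and 90% power two-sided would take 32 pairs.

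**Step 3: the 80% sentence.** Divide each difference by its SD, then apply the same formula.

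| Difference / SD | Effect (SD) | Power, one-sided 0.1 | Power, two-sided 0.1 |
|---|---|---|---|
| 0.13 / 0.25 | 0.52 | 89.8% | 81.1% |
| 0.27 / 0.50 | 0.54 | 91.5% | 83.6% |
| 0.40 / 0.75 | 0.533 | 91.0% | 82.8% |

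The 80% is out of line with one-sided 0.1 in all three rows and in line with two-sided 0.1. At these effect sizes one-sided 0.05 gives the same power as two-sided 0.1, so the figures alone cannot say which of those two was meant. At one-sided 0.1, 80% power would correspond to 0.43 SD, that is, differences of about 11%, 22% and 32%.

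**Step 4: whether the McNemar figures are really two-sided.** Write p for the sum of the two discordant proportions and δ for their difference. The normal approximation is power = Φ[(δ√n − z√p) / √(p − δ²)].

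- Table 1a: δ = 0.35, p = 0.55. Two-sided 0.1 gives 79.1%; one-sided 0.1 would give 88.9%.
- Table 1b: δ = 0.40, p = 0.60. Two-sided 0.1 gives 86.3%; one-sided 0.1 would give 93.6%.

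The stated 79% and 86% match the two-sided results, so that half of the section follows its label.

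**The case against.** The strongest reply is that nothing printed beside the 90% is false. The sentence declares a one-sided test at 0.1, and the number is right for that test. One-sided planning is also normal in this trial: the primary PFS test in Section 9.1.1 is one-sided at 0.2. Tables 1a and 1b both illustrate a rise in strong staining, from 0.40 to 0.75 or 0.80, which suggests the expected direction. Further, the one-sided label sits on the power sentence and not on the sentence that names the analysis, so it may be only a planning assumption.

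Much of this stands. The 90% is not a miscalculation, and declaring a direction would be an acceptable remedy. But the PFS test has a clear direction (5.5 to 7.3 months), whereas the tables only illustrate a rise under an explicitly two-sided test. If the label is merely a planning assumption, the power quoted is not that of the analysis described. None of it explains the 80% sentence.

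A reader might also infer three stronger things that the documents do not support:

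- **That the false-positive rate is 20% per marker.** This would follow only if the direction were picked after seeing the data, and nothing in the plan proposes that. With a direction fixed in advance, the one-sided t-test and the two-sided McNemar test each have a total error rate of 10%.
- **That a fall in a marker would go unseen.** The section also commits to descriptive statistics for the change from pre-treatment to on-treatment, so a fall would be reported whatever the p-value.
- **That all Section 8 markers will be tested one-sided.** The plan says only that their analyses will be similar; it states neither sidedness nor alpha for them.

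**Conclusion.** The point holds as an inconsistency in specification, not as an arithmetic error. Section 9.1.3 leaves the direction of a one-sided test unstated and attaches 90% and then 80% power to essentially one effect with the same 25 pairs. Both cannot be true at one-sided 0.1. Reading the t-test as two-sided at 0.1 brings it into line with the non-directional objective and McNemar's test, and broadly with the 80% sentence (81 to 84%). The cost is about 8 points against the headline figure (90.7% to 82.4%).

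This rests on 25 complete pairs, on approximate normality of the paired differences, and on reading the 80% sentence as the same paired t-test, which its context supports but its wording does not spell out. That the question is two-sided is inferred from the objective and from McNemar's alternative.

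The consequence is small. The endpoints are exploratory, the 25 pairs are an expected yield and not a number derived from power, and no sample size, go/no-go rule, or primary or secondary conclusion changes.

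**What to change.** In Section 9.1.3, specify the paired t-test, and any non-parametric substitute, as two-sided at alpha 0.1, as for McNemar's test. Restate its power with 25 pairs as 82% for 0.53 SD, or 90% for 0.60 SD. Label the 13%/27%/40% sentence as two-sided alpha 0.1, with power of 81 to 84%. State the sidedness for the Section 8 markers too, so that it need not be inferred.

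If the sponsor prefers a one-sided test, the alternative is to pre-specify and justify the direction separately for CD8 and for PDL1, and to correct the 80% to about 90%.

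Either route is a few lines of text, with no extra patients, biopsies or procedures. The two-sided route has a lower stated power, and a real loss of power if the change is in the direction the sponsor expects.

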8.2 Circulating Immune Cells (PBMC)

Peripheral blood will be collected for peripheral blood mononuclear cells (PBMCs) from each subject at the following timepoints: baseline, end of monotherapy lead-in on Day 8 (biomarker cycle of dose

expansion cohort only), end of first cycle of combination therapy on Day 29 (biomarker cycle of dose expansion cohort only), first restaging only, disease progression or treatment discontinuation, and for complete responders on long term follow-up. Refer to *Study Manual* for collection and submission details.

PBMCs will be processed and stored by the Duke Immune Profiling Core facility under the direction of [name]. Polychromatic flow cytometry (PFC) panels will be used to compare treatment related changes in both tumor and peripheral immune cell compartments. Up to 50 markers may be analyzed using 3 PFC panels: 1) a 12-color 'Exhaustion Panel', 2) a 12-color 'Tumor Reactive T Cell Panel', and 3) a 14-color regulatory T cell (Treg) and myeloid-derived suppressor cells (MDSC) panel. This analysis will be overseen by [name].

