8.6.2 Duke – Olink Collaboration

In order to identify potential mechanisms of sensitivity and resistance to pembrolizumab in gastric cancer and to better characterize the changes of key tumor and immune factors in response to pembrolizumab therapy, we plan to collaborate with Olink for both tissue- and blood-based biomarker analyses using their comprehensive, state-of-the-art technology platforms (<https://www.olink.com/>)

8.6.2.1 The following samples for the specified assays and analytic pipelines will be shared with Olink.

Sample Type	Sample Format/Quantity	Assay Type
Fresh frozen tumor tissue 25 samples	Tissue lysate, 20 ug per sample	Olink Explore 1536
PBMC 150 samples	Cell lysate, 1000 PBMCs per sample	Olink Explore 1536
Plasma 150 samples	100 µl per sample	Olink Explore 1536

8.6.2.2 The following clinical data will be shared with Olink in order to utilize pre-existing biomarker analytic pipelines. Duke statisticians will work with both teams in a collaborative fashion to analyze and interpret the data from each project.

- Deidentified patient metadata.
 - Patient age, gender, race/ethnicity, prior therapies, treatment duration, treatment dosage, smoking status, tumor size, tumor site
- RECIST and iRECIST response data for each patient case per timepoint
- Deidentified patient outcomes data.
 - OS, PFS and response to therapy

No personal health information will be shared with Olink.

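### The no-adjustment rule for biomarkers also covers the high-plex panels, where at alpha 0.1 about 10% of unchanged markers would be flagged per contrast with no multiplicity measure reported

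*Combined protocol and SAP*

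**What the plan says.** Section 9.1.3 opens with "CD8 and PDL1 staining measured by IHC are the primary biomarker endpoints for this study". For these two it plans a paired t-test, with power given at one-sided alpha 0.1, and McNemar's test, with power given at two-sided alpha 0.1. On sample size it says "We expect approximately 25 patients to have paired measurements".

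After the two McNemar tables it continues: "Similar analyses will be conducted for other biomarkers as described in Section 8.0". The next sentence is "No adjustments will be made for multiple comparisons". Nothing limits that sentence to CD8 and PDL1.

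Section 8.0 is wide:

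- Section 8.2 (PBMC): "Up to 50 markers may be analyzed using 3 PFC panels".
- Section 8.6.2 names "Olink Explore 1536" as the assay for 25 frozen tumor samples, 150 PBMC samples and 150 plasma samples.
- The opening paragraph of Section 8.0 leaves the final choice of analytes and platforms open.

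The documents set no false discovery rate, ranking rule, validation step or reporting caveat for these panels. Sections 8.6.1 and 8.6.2 say that outcome data go to the two outside collaborators so that analysis pipelines already in place can be used, with the Duke statisticians taking part. They do not say how those pipelines handle multiplicity.

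**The concern.** Leaving two named endpoints unadjusted is reasonable. The same sentence, read as written, also covers dozens of flow markers and possibly more than a thousand proteins, each of which can be tested in several ways. Section 8.3 has plasma drawn at baseline, Day 8, Day 29, each restaging and later, and has both levels and changes related to PFS and OS.

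The stated purpose of the two collaborations is to find mechanisms of sensitivity and resistance. That needs some way to judge which flagged markers deserve follow-up. A raw p-value below 0.1, without the number of markers tested or a q-value, gives little help with that judgement.

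**Working it through.** **Inputs.** From Section 9.1.3: about 25 pairs, a change of 0.53 SD, alpha 0.1. From Section 8.2: up to 50 flow markers. From Section 8.6.2: the platform name only; 1536 assays is an assumption read from that name. The share of markers that truly change, *p*, is not in the documents and is varied below. Carrying alpha 0.1 to these platforms is an inference from the instruction to run similar analyses.

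**1. The plan's own figures.** The plan says "With 25 patients studied a difference of 0.53 standard deviation (SD) can be detected with 90% power" at one-sided alpha 0.1. The noncentrality is 0.53 × √25 = 2.65 on 24 degrees of freedom, which gives power 90.7% (normal approximation 91.4%). The McNemar figures also reproduce by the unconditional normal approximation at two-sided alpha 0.1: 79.1% against a stated 79% for Table 1a, and 86.3% against 86% for Table 1b.

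**2. False positives when nothing changes.** Expected number = *m* × alpha. This holds whether or not the markers are correlated.

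| Markers tested, *m* | alpha 0.1 | alpha 0.05 |
|---|---|---|
| 2 (CD8, PDL1) | 0.2 | 0.1 |
| 50 | 5.0 | 2.5 |
| 1536 | 153.6 | 76.8 |

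These counts are per contrast. If all three sample types in Section 8.6.2 were measured on 1536 assays, one contrast would involve 3 × 1536 = 4608 tests.

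**3. Share of flagged markers that is false.** False share = alpha(1 − *p*) / [alpha(1 − *p*) + power × *p*]. With alpha 0.1 one-sided, power 0.907 and *p* = 5%, this is 0.095 / (0.095 + 0.0454) = 68%. The counts below are for 1536 assays.

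| *p* | False hits | True hits | False share |
|---|---|---|---|
| 1% | 152 | 14 | 92% |
| 5% | 146 | 70 | 68% |
| 10% | 138 | 139 | 50% |
| 20% | 123 | 279 | 31% |
| 30% | 108 | 418 | 20% |
| 50% | 77 | 697 | 10% |

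False and true hits are equal at *p* = alpha / (alpha + power) = 0.1 / 1.007, about 10%. For smaller true changes the break-even share rises to about 15% at 0.3 SD (power 57.6%) and 21% at 0.2 SD (power 38.3%).

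**4. Other test settings.** At two-sided alpha 0.1 (power 82.4%) the false share is 70%, 52% and 33% for *p* of 5%, 10% and 20%. At two-sided alpha 0.05 (power 72.0%) it is 57%, 38% and 22%. In frozen tissue, 25 samples allow at most 12 pre/on-treatment pairs. Power there is below the 25-pair figure, and the false share is higher.

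**5. What strict control would cost.** With 25 pairs and 0.53 SD, Bonferroni at an overall one-sided 0.1 cuts power from 91% to 33% for 50 markers (0.1/50 = 0.002 per test) and to 6% for 1536 (0.1/1536 = 0.000065). Holding the expected false share at 10% with two-sided tests leaves power of about 18%, 33%, 51% and 64% if 5%, 10%, 20% and 30% of markers change.

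**The case against.** The best defence is that this is openly exploratory work. It sits under exploratory objectives and endpoints, no dose or efficacy decision depends on it, and the absence of adjustment is disclosed. Unadjusted screening is a recognised choice when the aim is to generate hypotheses. That stands: no confirmatory error rate is breached, and the point is about usefulness, not validity.

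The inputs are also soft. The plan says similar analyses, not identical ones, and alpha 0.1 appears only in power statements for CD8 and PDL1. The flow count is an upper limit, the protein count comes from a product name, and the analyte list is open. For the protein platform, the collaborator's pipeline may control error. All of this stands, so the counts in the working are conditional. The sentence on adjustment, however, makes no exception for these data.

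A reader might go further and infer that false hits will swamp real ones. The documents do not support that. It requires a small share of truly changing markers, and no share is given; above about 10% at 0.53 SD, true hits are the majority. A reader might also infer that the resulting lists cannot be interpreted at all. That is too strong, because anyone who knows how many markers were tested can work out the expected false count.

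Lastly, adjustment costs power. With about 25 pairs the loss in step 5 is real, and it argues against requiring a fixed cutoff before a marker may be called a finding.

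**Conclusion.** The point holds at low severity. As written, Section 9.1.3 applies a rule suited to two endpoints to panels of up to 50 and perhaps 1536 markers. If alpha 0.1 goes with it, about 10% of unchanged markers will be flagged per contrast.

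The false share of what is flagged is not knowable from the documents. It runs from about 68% to 31% as the share of truly changing markers goes from 5% to 20%, assuming 25 pairs, a true change of 0.53 SD and one-sided tests. The expected counts do not require independent markers. They do rest on the alpha carried over and, for the protein platform, on the assumed assay count.

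**What to change.** Confine the no-adjustment sentence in Section 9.1.3 to CD8 and PDL1. For each multi-marker platform, replace it with a reporting rule that:

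- states the number of markers tested in each contrast;
- gives Benjamini-Hochberg q-values beside the raw p-values;
- labels markers with high q-values as hypothesis-generating only.

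The same rule should apply to results that come from the collaborators' pipelines. No fixed false discovery rate cutoff need be imposed.

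The cost is a sentence or two in the analysis section and one computed column per table. Data collection, sample size and the primary analysis are unchanged. The downside is that fewer markers will look convincing. Because the raw p-values stay visible, no exploratory signal is lost.
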